5.2. Exclusion criteria

- 1. Hemorrhage diseases according to head CT, such as hemorrhagic stroke, epidural hematoma, intracranial hematoma, intraventricular hemorrhage, subarachnoid hemorrhage and hemorrhage after cerebral infarction;
- 2. Transient ischemic attack (TIA);
- 3. Severe disturbance of consciousness: 1a of NIHSS score >1 point; Difficulty in swallowing, unable to take oral capsules; any of 5a, 5b, 6a, 6b of NIHSS score >2 point.

- 4. Convinced of stroke caused by brain tumor, brain trauma, hemopathy, etc.;
- 5. Hemorrhagic tendency patients;
- 6. Patients with endovascular treatment after the onset of stroke;
- 7. Patients with dementia, severe Parkinson's disease, mental disorders, limb dysfunction caused by other diseases or other conditions that may affect the efficacy determination;
- 8. Uncontrolled hypertension (≥200 mmHg systolic or ≥110 mmHg diastolic) or hypotension (≤90 mmHg systolic or ≤60 mmHg diastolic); severe hyperglycemia (blood glucose ≥400 mg/dL)
 - (22.2 mol/L) or hypoglycemia (blood glucose ≤50 mg/dL) (2.8 mol/L);
- 9. Severe hepatic insufficiency defined as transaminase values >2x upper limit of normal; severe renal insufficiency defined as values serum creatinine >1.5x upper limit of normal; cardiac dysfunction or other serious systemic disease with life expectancy ≤3 months;
- 10. Patients with concurrent malignancy or ongoing anti-tumor therapy;
- 11. Patients with history of being allergic to study drug and control drug;
- 12. Pregnancy, breastfeeding or potential pregnancy;
- 13. Within three months or currently participating in another investigational study;
- 14. Any other condition that in the opinion of the investigator should preclude study participation.

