6.1.6.2 Definite indications for discontinuing study drug

Patients should discontinue the study drug in the following circumstances:

Clinical conditions necessitating discontinuation of the drug (e.g., abnormal laboratory values)

Pregnancy or a desire to become pregnant

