7.1.2 Secondary efficacy endpoint

1. Improvement in neurological deficit (proportion of patients with NIHSS ≤1 or NIHSS improved by 4 points or more)

- 2. Improvement in activities of daily living (proportion of patients with BI index \geq 85)
- 3. Disability rate (proportion of patients with mRS score \geq 3 points);
- 4. Continuous changes of mRS scores;
- 5. Incidence of ischemic cerebrovascular disease during follow-up;
- 6. Incidence of combined vascular events during follow-up;

7.2 Safety indicators:

- Adverse event assessment
- Clinical laboratory indicators include blood routine (hemoglobin, red blood cells, white blood cells, platelets), urine routine (urine protein, urine white blood cells, urine red blood cells), serum biochemistry (alanine aminotransferase, aspartate aminotransferase, alkaline phosphatase, glutamine, urea nitrogen, creatinine, total bilirubin, blood glucose, total cholesterol, triglycerides, low-density lipoprotein, high-density lipoprotein).
- Coagulogram: Coagulation 4-item (PT, APTT, TT, FIB)
- 12-lead ECG
- Physical examination

8 Study Process

Refer to Table 1 for details of the study process.

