10.5 Operational procedures

- (1) In the process of drug clinical study, personnel at all positions have their own responsibilities and duties, and perform their tasks in accordance with the regulations.
- (2) Strictly adhere to the standard operating procedures at each stage of the drug clinical study.
- (3) During the drug clinical study, study staff should closely observe or follow up on various reactions occurring in subjects after drug administration, in order to promptly detect adverse events or serious adverse events and provide timely intervention.
- (4) During the drug clinical study, once a subject experiences an adverse reaction, regardless of its causal relationship with the study drug, the investigator should record all adverse events in the original records and sign them. If it is an adverse drug reaction, a preliminary assessment and diagnosis or suspected diagnosis of the adverse reaction should be made based on the criteria for determining the causality between adverse drug reactions and the drug.
- (5) For subjects experiencing common adverse reactions to the study drug, the investigator should immediately report to the PI, determine necessary diagnostic and treatment measures based on the condition, decide whether to discontinue the clinical study, follow up and investigate all adverse events, record the detailed process and outcomes until the issue is resolved or the condition stabilizes. If there are laboratory abnormalities, follow-up should continue until recovery to normal. The follow-up method can be chosen based on the severity of the adverse reactions, including options such as hospitalization, outpatient visits, home visits, phone calls, and communication.
- (6) In the case of serious adverse events, the doctor should immediately initiate rescue according to the Emergency Response SOP and record it. Consultation with relevant specialized departments should be requested, and in cases of urgency, the subject should be urgently transported to the ICU for treatment, accompanied by medical staff. In addition, the PI should be immediately notified, and the Subject Injury and Adverse Event Handling Team should be promptly informed. During holidays, hospital on-call personnel should be notified, and reporting should be escalated as appropriate. The emergency response flowchart can be found in Appendix 5.

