The primary indicator will be assessed using a superiority test, testing the following hypothesis:

$$H_0: \pi_{Test\ group} - \pi_{Control\ group} \le 0$$

$$H_1: \pi_{Test\ group} - \pi_{Control\ group} > 0$$

$$\alpha = 0.025 (One - sided)$$

If the H_0 is rejected at the significance α level, or if the lower limit of the 95% CI for the difference in retention rates between the two groups is greater than 0, it can be considered that the treatment group is superior to the control group.

Other secondary indicators will be compared using the same statistical method as the primary indicator.

12.2.4. Safety evaluation:

Describe the number and proportion of subjects with normal values before treatment and abnormal values after treatment for both the treatment group and the control group separately. Describe adverse events using the number of cases, the number of subjects, and the incidence rate. Conduct inter-group significance tests will be conducted on the incidence rate. Additionally, provide a detailed description of the specific manifestations, severity, and the relationship with the drug for all adverse events observed in each group. Provide a cross-tabular description of the changes in laboratory indicators before and after the treatment. Compare vital sign indicators before and after the treatment.

13 Data Management

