6.2.5 Safety analysis

Adverse events are described with case number, times and incidence of various adverse events, and $\chi 2$ test or Fisher's exact test is adopted for comparing the incidence between the two groups. At the same time, make a detailed list to describe the specific manifestation and extent of all adverse events and serious adverse events and their relation with drugs.

Statistically describe the vital signs at baseline and 90 days after treatment according to general principles, and make comparison between former and later times and inter-group comparison.

Make description of number of normal cases before treatment, number abnormal cases after treatment and their ratios in two groups, respectively, and $\chi 2$ test or Fisher's exact test is adopted for comparing the ratio between the two groups.

Make description of number of normal cases before treatment, number abnormal cases after treatment and their ratios in two groups, respectively, and $\chi 2$ test or Fisher's exact test is adopted for comparing the ratio between the two groups. Crosstab is adopted to describe the change of laboratory indexes before and after treatment for determining the clinical significance of these indexes.

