7.4.3 Laboratory indexes

Table 7.4.3.1 Numbers and percentages of cases with normal laboratory indexes before treatment and abnormal laboratory indexes after treatment (SS) – blood routine test

	Treatment group		Control group		
Item	Case number	Percentage	Case number	Percentage	P value
Red blood cell -abnormal but					
without clinical significance					
Red blood cell -abnormal and with					
clinical significance					
White blood cell - abnormal but					
without clinical significance					
White blood cell - abnormal and					
with clinical significance					
Hemoglobin - abnormal but without					
clinical significance					
Hemoglobin - abnormal and with					
clinical significance					
Platelet count - abnormal but					
without clinical significance					
Platelet count - abnormal and with					
clinical significance					

Table 7.4.3.2 Numbers and percentages of cases with normal laboratory indexes before treatment and abnormal laboratory indexes after treatment (SS)—routine urine test

Table 7.4.3.3 Numbers and percentages of cases with normal laboratory indexes before treatment and abnormal laboratory indexes after treatment (SS) – liver function

The same as above

Table 7.4.3.4 Numbers and percentages of cases with normal laboratory indexes before treatment and abnormal laboratory indexes after treatment (SS) – renal function

The same as above

Table 7.4.3.5 Numbers and percentages of cases with normal laboratory indexes before treatment and abnormal laboratory indexes after treatment (SS) – blood fat and blood glucose

The same as above

Table 7.4.3.6 Numbers and percentages of cases with normal laboratory indexes before treatment and abnormal laboratory indexes after treatment (SS) – four items of blood coagulation

The same as above

Table 7.4.3.7 Numbers and percentages of cases with normal laboratory indexes before treatment and abnormal laboratory indexes after treatment (SS) – ECG

	Treatment group		Control group		
Item	Case number	Percentage	Case number	Percentage	P value
Abnormal Q wave					
Abnormal T wave					
Arrhythmia – atrial fibrillation					
Arrhythmia –ventricular premature					
beat					
Arrhythmia - ventricular					
tachycardia					
Arrhythmia - atrioventricular block					
/ bundle branch block					
Arrhythmia – other					
Others					
Number of cases with normal ECG					
before treatment and abnormal ECC	Ī				
after treatment					

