Table 7.4.3.20 Crosstab for determining clincial significance of laboratory indexes before and after treatment (SS) –routine urine test – urine protein – treatment group

The same as above

Table 7.4.3.21 Crosstab for determining clincial significance of laboratory indexes before and after treatment (SS) –routine urine test – urine protein – control group

Table 7.4.3.22 Crosstab for determining clincial significance of laboratory indexes before and after treatment (SS) – liver function – AST – treatment group

Table 7.4.3.23 Crosstab for determining clincial significance of laboratory indexes before and after treatment (SS) – liver function – AST – control group

Table 7.4.3.24 Crosstab for determining clincial significance of laboratory indexes before and after treatment (SS) – liver function – AST – treatment group

The same as above

Table 7.4.3.25 Crosstab for determining clincial significance of laboratory indexes before and after treatment (SS) – liver function – AST – control group

Table 7.4.3.26 Crosstab for determining clincial significance of laboratory indexes before and after treatment (SS) – liver function – ALP – treatment group

The same as above

Table 7.4.3.27 Crosstab for determining clincial significance of laboratory indexes before and after treatment (SS) – liver function – ALP – control group

Table 7.4.3.28 Crosstab for determining clincial significance of laboratory indexes before and after treatment (SS) – liver function – TBIL – treatment group

The same as above

Table 7.4.3.29 Crosstab for determining clincial significance of laboratory indexes before and after treatment (SS) – liver function – TBIL – control group

Table 7.4.3.30 Crosstab for determining clincial significance of laboratory indexes before and after treatment (SS) – liver function – GGT – treatment group

The same as above

Table 7.4.3.31 Crosstab for determining clincial significance of laboratory indexes before and after treatment (SS) – liver function – GGT – control group

Table 7.4.3.32 Crosstab for determining clincial significance of laboratory indexes before and after treatment (SS) – renal function – BUN/UREA – treatment group

The same as above

Table 7.4.3.33 Crosstab for determining clincial significance of laboratory indexes before and after treatment (SS) – renal function – BUN/UREA – control group

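### The only between-arm test of laboratory values counts normal-to-abnormal change at one undefined post-treatment point; worsening from an abnormal baseline is described but not tested, and discharge results are not used

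*Combined protocol and SAP*

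**What the plan says.** The protocol, section 12.2.4, describes laboratory safety as follows: "Describe the number and proportion of subjects with normal values before treatment and abnormal values after treatment". It gives no test for this. SAP 6.2.5 repeats the idea and adds a chi-square or Fisher comparison: "Make description of number of normal cases before treatment, number abnormal cases after treatment and their ratios in two groups". The matching shells, Tables 7.4.3.1 to 7.4.3.6, have a P value column and list only patients who move from normal to abnormal, split by clinical significance.

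SAP 6.2.5 then adds a before/after crosstab for each analyte and arm (Tables 7.4.3.8 onward). The rows and columns are normal, abnormal without clinical significance, abnormal with clinical significance, unchecked and lost. These shells have no P value.

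Other relevant places:
- Protocol 5.2 excludes "Severe hepatic insufficiency defined as transaminase values >2x upper limit of normal", and creatinine only above 1.5 times ULN, so milder abnormalities are eligible.
- The flowcharts (protocol Appendix 1, SAP 4.1.3) mark laboratory tests with a filled symbol at screening and Day 90 and an open symbol at discharge and at the optional Visit 5. Protocol 8.3 says that the discharge results are to be gathered for safety.
- SAP 6.1.3 does not carry safety values forward.
- Protocol 10.5, on handling adverse events, says: "If there are laboratory abnormalities, follow-up should continue until recovery to normal".
- Protocol 10.7 records a clinically significant abnormal result as an adverse event in its own right if it is symptomatic, changes study medication, or requires a change in other treatment.

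**The concern.** A laboratory safety analysis should detect patients whose values get worse on treatment, whatever their starting value and whenever it happens. The tested table here can register only one kind of worsening, at one time.

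Two groups lie outside it. The first is patients who enter with a mildly abnormal value and deteriorate. A patient who goes from 1.8 to 10 times ULN is not a normal-to-abnormal case. The second is patients with an abnormality during treatment that has resolved by the visit that supplies the post-treatment value. Medication safety is a stated secondary objective in both documents, so a reader will lean on these tables for hepatic, renal and glucose markers.

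The table list also has errors. Tables 7.4.3.22 to 7.4.3.25 print "liver function – AST – treatment group" and its control-group counterpart twice and never name ALT, which is measured. Tables 7.4.3.30 and 7.4.3.31 are for GGT, but the measured lists (protocol 7.2 and 9.2, SAP 5.3) omit GGT and name glutamine, as in "alkaline phosphatase, glutamine, urea nitrogen".

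**Working it through.** The plan gives no figure to reproduce for this point: it states no baseline abnormality rate, no expected rate of worsening and no power for a safety comparison. The main check is therefore to follow patients through the planned tables.

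**1. Which visit?** SAP 6.2.5 names baseline and 90 days for vital signs but no visit for laboratory values. Day 90 is the natural reading, because that is where the flowcharts require the tests. It is an inference.

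**2. Which denominator?** SAP 6.1.3 makes the safety set the denominator for adverse event incidence. For the normal-to-abnormal percentage nothing is stated. It could be all safety-set patients, those normal at baseline, or those normal at baseline with a post-treatment result.

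**3. Where each type of patient appears, taking Day 90 as the post-treatment visit:**

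| Patient | Tested table | Crosstab (untested) | Adverse event table (tested) |
|---|---|---|---|
| Normal at baseline, abnormal at Day 90 | Counted | Shown | If 10.7 is met |
| Abnormal, not clinically significant, becoming significant | Not counted | Shown | If 10.7 is met |
| Worse within the same abnormal category | Not counted | Same cell | If 10.7 is met |
| Normal, abnormal at discharge, normal at Day 90 | Not counted | Normal to normal | If 10.7 is met |
| Abnormal during treatment, no Day 90 test | Not counted | Unchecked or lost | If 10.7 is met |

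The last column is the only tested route for the lower four rows. It needs an investigator's judgement of clinical significance plus one of the three conditions in 10.7. An asymptomatic rise on which nobody acts need not qualify.

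**4. Illustration on assumed rates.** None of these rates comes from the documents. Take 984 patients per arm (the planned enrolment), a proportion q abnormal at baseline, and these worsening risks:
- normal baseline: treated 5%, control 3%
- abnormal baseline: treated 10%, control 6%

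Share of treated-arm worsening outside the tested table = 0.10q / [0.05(1 − q) + 0.10q].
- q = 10%: 0.010 / (0.045 + 0.010) = 18%
- q = 40%: 0.040 / (0.030 + 0.040) = 57%

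Power, two-sided 0.05, normal approximation:

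| q | Normal baseline only (n per arm) | Any worsening, all 984 per arm (risks control, treated) |
|---|---|---|
| 10% | 57.5% (886) | 66.3% (3.3%, 5.5%) |
| 40% | 41.8% (590) | 77.1% (4.2%, 7.0%) |

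The overall risks are weighted averages; for q = 10% in the treated arm, 0.9 × 5% + 0.1 × 10% = 5.5%. The illustration shows that the gap could matter. It does not estimate the gap in this trial, and it does not model the loss from transient abnormalities.

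**The case against.** The strongest reply is that the laboratory tables are not the whole safety plan. A reader might infer that patients who enter abnormal and worsen, or who stop for a laboratory abnormality and recover, are never counted as harmed. The documents do not support that. A clinically significant abnormality that changes study medication is an adverse event under protocol 10.7, whatever the Day 90 value. Adverse event incidence is tested between arms, and Table 7.4.1.1 has rows for drug-related events and for events that led to drop-out. The instruction to follow laboratory abnormalities to recovery itself sits in the adverse event procedures. The crosstabs also show, by arm, moves from one abnormal category to the other. This part of the reply stands.

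A reader might also infer bias towards no drug effect. That is not shown. Baseline status precedes treatment, so restricting to normal baselines mainly loses information and power. Dilution by recovered values is possible but cannot be quantified. Nor is everyone withdrawn for a resolved abnormality scored as normal to normal: some start abnormal and some will have no Day 90 test. Protocol 6.1.6.3 requires the three-month endpoint follow-up after stopping drug but does not say that blood is drawn.

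It is tempting to size the gap with the roughly 40% post-stroke hyperglycaemia in protocol Appendix 7. That is guideline background on stroke patients generally. It is not a baseline rate for this eligible population, which is sampled fasting.

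The AST and glutamine entries may well be translation slips. They still need correcting, because tables are programmed from them.

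What the reply leaves untouched is that no tested comparison of the laboratory values covers worsening from an abnormal baseline, and no table uses the discharge results. The adverse event table has pooled rows only, with none for hepatic or renal events.

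**Conclusion.** The point holds as a limitation of the laboratory tables, with medium confidence. The tested comparison covers only normal-to-abnormal change at one point whose visit and denominator are undefined. Worsening from an abnormal baseline is described without a test, in categories that hide worsening within a category. If post-treatment means Day 90, an abnormality that has resolved by then shows in no laboratory table and depends on adverse event reporting.

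The consequence is reduced sensitivity to laboratory harm. The documents do not allow its size to be calculated; the 18% to 57% range rests wholly on assumed rates. It does not follow that harmed patients go uncounted in the trial, or that the comparison is biased towards no effect. This is an improvement that should be made because it is cheap. It does not invalidate the safety plan.

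**What to change.** In SAP 6.2.5 and Tables 7.4.3.x:

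1. State the visit and the denominator of the normal-to-abnormal tables, and keep those tables as supportive.
2. Add a between-arm comparison of worsening from any baseline, in all safety-set patients with a baseline and at least one post-baseline value. Use the worst post-baseline value from Visits 3, 4 and 5 and unscheduled tests. Define worsening by pre-specified numeric multiples of ULN or of baseline, or by worsening of category if the database holds only categories.
3. Change one AST pair in Tables 7.4.3.22 to 7.4.3.25 to ALT.
4. Make the measured list (glutamine) and the planned GGT tables agree.

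The cost is SAP wording, a few more tables and their programming. Numeric values may have to be entered from the laboratory reports, which protocol section 14 requires to be documented or pasted onto the case report forms. No new patient procedure is needed. Discharge data will be incomplete, because protocol 8.3 treats those tests as routine care that the study does not fund, so the number of patients contributing at each visit should be reported by arm. The reported abnormality rate may rise in both arms.

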6.2.6 Exploratory analysis

Take predicted subgroup analysis on primary indexes;

7. Results of statistical analysis

7.1 Completion of study

7.1.1 Distribution of cases

Table 7.1.1.1 Distribution and grouping of cases

		Number of	Number of		
Center	Group	enrolled cases	drop-out cases	Drop-out ratio (%)	Completion
1Center	Treatment group				
	Control group				
	Total				
2 Center	Treatment group				
	Control group				
	Total				
•••	•••				
Total	Treatment group				
	Control group				
	Total				

Table 7.1.1.2 Completion of study, safety analysis set and efficiency analysis set

	Treatment		
Item	group	Control group	Total

Completion of enrollment

Random grouping

Completed study

Uncompleted study

Main reasons for suspending the study

Inconsistent with inclusion criteria or conform to exclusion

criteria

Have adverse event

Lack of efficacy and drop out

Violate study programme

Cancellation of informed consent

Have serious concomitant disease in the course of study

Loss to follow-up or not take follow-up in time

Other reason

Analysis set

FAS

PPS

SS

Table 7.1.1.3 List of drop-out and excluded patients

Contor	No	Group	EVC	DDC	66	Dancon of drop out
Center	No.	Group	IAS	LLD	သ	Reason of drop-out

Table 7.1.1.4 Distribution of population

	FAS			PPS			SS		
	Treatment	Control		Treatment	Control		Treatment	Control	
Center	group	group	Total	group	group	Total	group	group	Total
1 Center									
2 Center									
Total									

